## 5.2. FINAL ANALYSIS

All final, planned analyses identified in this SAP will be performed by Quintiles Biostatistics following sponsor authorization of this statistical analysis plan and analysis sets. The final analyses will be performed following the sponsor-authorized SAP and analysis sets for the clinical study report (CSR).

## 6. ANALYSIS SETS

Analysis of efficacy and safety endpoints will be performed based on the analysis sets defined in this section and as specified for each endpoint throughout this SAP.

Subjects will be classified in treatment groups based on whether they received teduglutide in the core study TED-C13-003 (as 0.0125 mg/kg/day, 0.025 mg/kg or 0.05 mg/kg) and/or during the prospective observation period in this study:

- TED/NTT – includes subjects who took teduglutide in the core study but not in the extension study;
- TED/TED – includes subjects who took teduglutide in the core study and in the extension study;
- ANY TED – includes subjects who took teduglutide in either the core study or in extension study.

No treatment-naïve patients in core study TED-C13-003 enrolled in the extension study SHP633-303, so the treatment groups associated with the NTT in the core study are removed from the statistical analysis.

---

Document: \\quintiles.net\Enterprise\Apps\sasdata\SASa\sas\Shire\Teduglutide\ZXA48914\Biostatistics\Documentation\SAP\SHP633-303\_SAP\_Draft\_V1.0\_20171023

Author: [REDACTED] Version Number: Draft V1.2  
Version Date: 16Jan2018

Template No: CS\_TP\_BS016 – Revision 3  
Effective Date: 01May2012

Reference: CS\_WI\_BS005

Copyright © 2012 Quintiles Transnational Corp. All rights reserved.  
The contents of this document are confidential and proprietary to Quintiles Transnational Corp. Unauthorized use, disclosure or reproduction is strictly prohibited.

## 6.1. ALL SUBJECTS SCREENED [SRN] SET

The all subjects screened (SRN) set will contain all subjects who provide signed informed consent for the study.

Data for subjects who fail to meet study inclusion eligibility criteria will be included in the listings but will not be included in any analyses.

## 6.2. SAFETY POPULATION

The safety population will contain all enrolled subjects who provided informed consent for the prospective portion and met all the inclusion criteria. Unless specified, the safety population will be used for both safety and efficacy analyses.

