### **8.3. MISSING DATA**

Missing data will in general not be imputed. However, partial dates will contribute to the analysis as described in Appendix 2. All available data will be included in the safety analysis.

Details for the imputation algorithm for the missing endpoint values for PS parameters (volume, calories and etc.) will be described in Section [16.1.1](#) of this analysis plan.

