## **10. DISPOSITION AND WITHDRAWALS**

All subjects who provide informed consent for prospective data collection in the extension study will be accounted for in the analyses. After signed consent (and informed assent, if applicable), a subject will be considered enrolled in the study if the subject meets all of the inclusion criteria at the screening. Teduglutide treatment eligibility does not impact study eligibility.

If the investigational product is discontinued prematurely during a teduglutide treatment cycle and the subject wishes to remain in the study, the evaluations listed for the EOT visit are to be performed. A 4-week follow-up period will ensue, consisting of weekly telephone visits (CxW25-27) and the week 28 clinic visit (CxW28). The subject would then enter a NTT period and could be evaluated for subsequent teduglutide treatment eligibility according to the study

Document:	\quintiles.net\Enterprise\Apps\sasdata\SASa\sas\Shire\Teduglutide\ZXA48914\Biostatistics\Documentation\SAP\SHP633-303_SAP_Draft_V1.0_20171023		
Author:	[REDACTED]	Version Number:	Draft V1.2

Template No: CS\_TP\_BS016 – Revision 3  
Effective Date: 01May2012

Reference: CS\_WI\_BS005

Version Date:  
16Jan2018

Copyright © 2012 Quintiles Transnational Corp. All rights reserved.  
The contents of this document are confidential and proprietary to Quintiles Transnational Corp. Unauthorized use, disclosure or reproduction is strictly prohibited.

schedules. The reason for permanent treatment discontinuation will be captured.

The reason(s) for permanent discontinuation of treatment and/or withdrawal from the study must be determined by the investigator, and recorded in the subject's medical record and in the electronic case report form (eCRF). If a subject is withdrawn for more than one reason, each reason should be documented in the source document, and the most clinically relevant reason should be entered in the eCRF. Overall reasons for discontinuation of treatment and withdrawal from study will be summarized separately based on the following categories:

- Adverse event
- Protocol deviation
- Lack of efficacy
- Physician decision
- Withdrawal by subject
- Withdrawal by parent/guardian
- Lost to follow-up
- Pregnancy
- Death
- Other

The ongoing subjects will be counted in the table for interim analysis.

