Protocol deviations as obtained from a clinical trial management system (CTMS) will be assessed throughout the study. All identified deviations will be reported in the CTMS. Protocol deviations from the CTMS will be coded to categories and provided as part of the CTMS transfer to Biostatistics. Protocol deviation categories from CTMS include:

1. Informed Consent Criteria
2. Eligibility and Entry Criteria
3. Concomitant Medication Criteria
4. Laboratory Assessment Criteria
5. Study Procedures Criteria
6. Serious Adverse Event Criteria
7. Randomization Criteria (Not applicable to this study)
8. Visit Schedule Criteria
9. Investigational Product Compliance

Document: \\quintiles.net\Enterprise\Apps\sasdata\SASa\sas\Shire\Teduglutide\ZXA48914\Biostatistics\Documentation\SAP\SHP633-303\_SAP\_Draft\_V1.0\_20171023

Author: [REDACTED]

Version Number:

Draft V1.2

Version Date:

16Jan2018

Template No: CS\_TP\_BS016 – Revision 3

Effective Date: 01May2012

Reference: CS\_WI\_BS005

Copyright © 2012 Quintiles Transnational Corp. All rights reserved.

The contents of this document are confidential and proprietary to Quintiles Transnational Corp. Unauthorized use, disclosure or reproduction is strictly prohibited.

---

- 10. Efficacy Criteria
- 11. Administrative Criteria
- 12. Source Document Criteria
- 13. Regulatory or Ethics Approvals Criteria
- 14. Other Criteria

The presentation of planned listings will include the following:

- Subject disposition (SRN set)
- Study Inclusion criteria violations (SRN set)
- Treatment Eligibility Criteria
- Follow-up Period Escape Criteria
- Protocol deviations

The following summary tables are planned for presentation:

- Subject disposition (SRN set)
- protocol deviations,

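### The prospective safety population is defined by meeting the study inclusion criteria, not by exposure or follow-up, so a followed subject later found ineligible would leave the summary tables

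*SAP*

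**What the plan says.** All references are to the prospective SAP (Draft V1.2).

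- Section 6.2 defines the set: "The safety population will contain all enrolled subjects who provided informed consent for the prospective portion and met all the inclusion criteria". It adds: "Unless specified, the safety population will be used for both safety and efficacy analyses". Section 16 confirms that efficacy is analysed on this population.
- Section 6.1, under the screened set, says: "Data for subjects who fail to meet study inclusion eligibility criteria will be included in the listings but will not be included in any analyses".
- Section 10 defines enrolment: "a subject will be considered enrolled in the study if the subject meets all of the inclusion criteria at the screening". It then separates the two kinds of eligibility: "Teduglutide treatment eligibility does not impact study eligibility".
- Section 10 also opens with a broad commitment: "All subjects who provide informed consent for prospective data collection in the extension study will be accounted for in the analyses".
- Section 3.1 gives long-term safety and tolerability as the primary objective.

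**The concern.** A safety set is normally built on who was exposed or observed. Here it is built on who was eligible, and no sentence keeps a subject who was treated or followed and only later found to have breached a study inclusion criterion. Such a child's adverse events, laboratory shifts, antibody results and parenteral support outcomes would be omitted from the tables for a reason that has nothing to do with whether harm occurred.

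What is at stake is the completeness of the incidence tables that answer the primary objective. The rule should be settled before anyone knows whom it removes. The document is still a draft, and section 5.1 plans an interim analysis of the prospective data to support a regulatory submission.

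**Working it through.** The plan gives no figure for this point, so there is nothing to reproduce. The check traces three kinds of subject through the wording and then gives an illustrative size.

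**Step 1. Trace through sections 6.1, 6.2 and 10.**

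- *Consented, failed a study criterion at screening, never followed.* Not enrolled under section 10, outside 6.2, listings only under 6.1. This is an ordinary screen failure and the outcome is reasonable.
- *Judged eligible at screening, entered a teduglutide cycle or NTT period, later found to violate a study criterion.* Section 10 ties enrolment to the criteria at screening. Section 6.2 requires enrolment and, in addition, that all the inclusion criteria were met, with no time qualifier. The subject fails that second condition, and 6.1 then allows listings only. If the later finding is held to undo enrolment as well, the subject is out on both counts. On neither reading is the subject kept.
- *Dosed in breach of a teduglutide treatment criterion, study criteria met.* Section 10 says treatment eligibility does not affect study eligibility. Section 4.1 asks for at least one treatment inclusion criterion, so the word *all* in 6.2 fits only the study list. This subject stays in.

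The gap is therefore confined to the second kind of subject.

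**Step 2. What that subject loses and keeps.** Lost: the summaries that use the safety population by default, namely adverse events (18.1), laboratory data (18.2), antibodies (18.4) and efficacy (16). Kept: the listings, including those for serious, fatal and special-interest events and for discontinuations, and the disposition table on the screened set (10).

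**Step 3. Illustrative size.** Input: about 40 expected subjects (section 4.1). That figure includes subjects who consent to retrospective collection only, so the prospective number is N ≤ 40 or so. The number of violators k is not given; k = 1 to 3 is an assumption. With n = N − k and N = 40:

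| k | n | share removed, k/N | upper one-sided 95% limit with 0 events, 1 − 0.05^(1/n) | chance of at least one case of a 5% event, 1 − 0.95^n |
|---|---|---|---|---|
| 0 | 40 | 0% | 7.22% | 0.8715 |
| 1 | 39 | 2.5% | 7.39% | 0.8647 |
| 2 | 38 | 5.0% | 7.58% | 0.8576 |
| 3 | 37 | 7.5% | 7.78% | 0.8501 |

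Because k/N rises as N falls, 2.5% per subject is a lower bound when N is below 40.

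If the excluded subject had an event, the tabulated incidence changes from e/40 to (e − 1)/39:

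- e = 1: 2.5% becomes 0%
- e = 2: 5.0% becomes 2.56%
- e = 4: 10.0% becomes 7.69%

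**The case against.** The strongest reply is that these sentences are about screen failures. The 6.1 exclusion stands under the screened set, and section 10 already makes the inclusion criteria part of being enrolled, so the clause in 6.2 may only repeat that definition. For 6.1 this reading is plausible. It does not settle 6.2, which adds the criteria on top of enrolment and without reference to screening. If the clause is mere repetition, it can be deleted at no cost.

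Other parts of the reply stand and limit the point. A reader might infer more than the document supports in five ways:

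- *That the subject vanishes from the report.* The listings and the disposition table keep the subject. Events of special interest are planned only as a listing, so their presentation does not change.
- *That any breach of a dosing criterion removes a child.* Only study inclusion criteria are at issue.
- *That the plan expects dosed violators.* The listing of inclusion violations is on the screened set, which holds screen failures by definition. The deviation categories are generic; one of them, randomization, is marked as not applicable.
- *That section 8.3 is flatly contradicted.* Its sentence, "All available data will be included in the safety analysis", stands among the missing-data rules and reads most naturally as concerning incomplete data, not membership of a set.
- *That 1/40 is the study's rate.* The figure of 40 is a ceiling for the prospective set.

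The section 10 commitment on consented subjects could arguably be met by the disposition table alone. It sits poorly with the exclusion but is not an outright contradiction.

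**Conclusion.** The point holds in a limited form. As written, sections 6.1 and 6.2 would leave a subject who was followed and later found to violate a study inclusion criterion out of the safety and efficacy summary tables, and nothing in the plan overrides this. That is a poor basis for the main analysis set of a safety study.

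The size rests on two unknowns: how many such subjects there are, possibly none, and how many subjects consent to the prospective portion, at most about 40. Each exclusion removes at least about 2.5% of subjects. The loss of precision is negligible: for one exclusion from 40, the zero-event upper limit moves from 7.22% to 7.39%. The analysis is descriptive and tests no hypothesis, so no formal inference is affected. The harm is selective: a rare event seen only in the excluded child would show as zero in the incidence table and be found only in a listing. The change should be made, but the document does not show that any exposed child has been or will be dropped.

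**What to change.** 1. In 6.2, define the safety population as all subjects who consented to the prospective portion and either received at least one teduglutide dose or entered an NTT period in SHP633-303, regardless of inclusion violations identified later.
2. In 6.1, limit the exclusion from analyses to screen failures who entered neither a teduglutide cycle nor an NTT period.
3. Keep the existing listing of study inclusion violations and report them as protocol deviations.
4. Wherever inclusion criteria are still mentioned in these sections, say that the study criteria are meant, not the teduglutide treatment criteria.

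The cost is SAP wording and the matching population flag in the programs. No new data are needed. If no such subject exists, no table changes.

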# 7. GENERAL CONSIDERATIONS

## 7.1. REFERENCE START DATE AND STUDY DAY

Study Day will be calculated from the reference start date, and will be used to show start/stop day of assessments and events. In addition, Day of Teduglutide Treatment will be calculated from the date of first dose of Teduglutide following signing of informed consent for the core study.

Reference start date of prospective period is defined as the start of the first cycle within the study, either treatment on Cycle 1 Day 1 for the teduglutide treatment period or the first date of the NTT period of SHP633-303. Note that the reference start date of core study TED-C13-003 is defined as the baseline visit of the extension study SHP633-303 for the efficacy variables. Study days before the reference start date will be negative.

If the date of the event is on or after the reference start date then:

$$\text{Study Day} = (\text{date of event} - \text{reference start date}) + 1.$$

If the date of the event is prior to the reference start date then:

$$\text{Study Day} = (\text{date of event} - \text{reference start date}).$$

In the situation where the event date is partial or missing, the date will appear partial or missing in the listings, and Study Day will be missing.

---

Document: \\quintiles.net\Enterprise\Apps\sasdata\SASa\sas\Shire\Teduglutide\ZXA48914\Biostatistics\Documentation\SAP\SHP633-303\_SAP\_Draft\_V1.0\_20171023

Author: [REDACTED]

Version Number:  
Version Date:

Draft V1.2  
16Jan2018

Template No: CS\_TP\_BS016 – Revision 3

Reference: CS\_WI\_BS005

Effective Date: 01May2012

Copyright © 2012 Quintiles Transnational Corp. All rights reserved.

The contents of this document are confidential and proprietary to Quintiles Transnational Corp. Unauthorized use, disclosure or reproduction is strictly prohibited.

## 7.2. BASELINE

Unless otherwise specified, baseline is defined as the last non-missing measurement on or prior to baseline visit in the core study TED-C13-003.

## 7.3. RETESTS, UNSCHEDULED VISITS AND EARLY TERMINATION DATA

In general, for by-visit summaries, data recorded at the nominal visit will be presented. Unscheduled measurements will not be included in by-visit summaries, but can contribute to the best/worst case value where applicable. Unscheduled PS prescription adjustments carry forward until the next adjustment, and as such, may contribute to data assigned to subsequent visits.

Listings will include scheduled, unscheduled, retest and early discontinuation data.

## 7.4. STUDY CYCLE CONVENTIONS

Visits will be summarized within the associated pretreatment period or treatment cycle or no treatment period. For teduglutide treatment cycles, Cycle x Day 1, Cycle x Week 1, ..., Cycle x Week 24, Cycle x Week 25 Follow-up, Cycle x Week 26 Follow-up, Cycle x Week 27 Follow-up and Cycle x Week 28 data will be collected according to the schedule of events.

For NTT periods, NTx data will be collected approximately every 12 weeks. Data for teduglutide treatment periods and NTT periods will be presented in separate tables.

## 7.5. WINDOWING CONVENTIONS

For teduglutide treatment period, nominal visits will occur within two days of the scheduled week 1, 2, 4 and 6 visits, within four days of the scheduled week 9 to week 24 visits and within two days of the follow-up visits week 25 to week 28 (EOS). For NTT period, nominal visits will occur within seven days of the scheduled 12-week intervals. There will be no windowing of scheduled visits based on study day, and unscheduled visits will not be included in by-visit summaries. Early termination data and end of treatment (EOT) visits with a teduglutide treatment cycle will be mapped to a scheduled visit if it falls into the appropriate visit window as defined in the protocol and if that scheduled visit did not occur. EOT visits, if occurring differently from week 24 will be tabled as a separate visit.

---

Document: \\quintiles.net\Enterprise\Apps\sasdata\SASa\sas\Shire\Teduglutide\ZXA48914\Biostatistics\Documentation\SAP\SHP633-303\_SAP\_Draft\_V1.0\_20171023

Author: [REDACTED] Version Number: Draft V1.2  
Version Date: 16Jan2018

Template No: CS\_TP\_BS016 – Revision 3  
Effective Date: 01May2012

Reference: CS\_WI\_BS005

Copyright © 2012 Quintiles Transnational Corp. All rights reserved.  
The contents of this document are confidential and proprietary to Quintiles Transnational Corp. Unauthorized use, disclosure or reproduction is strictly prohibited.

## 7.6. STATISTICAL TESTS

Due to the limited size of the study population, descriptive statistics will be used with a goal of summarizing the sample. As such, no claims of significance will be made for any of the data.

Continuous variables, including those assessed on a discrete scale, will be summarized using descriptive statistics including number of subjects, mean, median, standard deviation, maximum, and minimum. For categorical variables, statistical summaries will include number of subjects and percentages.

## 7.7. COMMON CALCULATIONS

For quantitative measurements, change from baseline will be calculated as:

Test Value at Visit X – Baseline Value

Percent change from baseline will be calculated as:

(Test Value at Visit X – Baseline Value) / Baseline Value \*100

Change (or percent change) from baseline tables will be calculated based on the number of subjects in the treatment group with a non-missing value at baseline and at the time point being analyzed.

## 7.8. SOFTWARE VERSION

All analyses will be conducted using SAS version 9.4 or higher.

# 8. STATISTICAL CONSIDERATIONS

## 8.1. ADJUSTMENTS FOR COVARIATES AND FACTORS TO BE INCLUDED IN ANALYSES

No adjustments for covariates are planned for the statistical analyses.

## 8.2. MULTI-CENTER STUDIES

This study will be conducted by multiple investigators at multiple centers internationally.

Document: \\quintiles.net\Enterprise\Apps\sasdata\SASa\sas\Shire\Teduglutide\ZXA48914\Biostatistics\Documentation\SAP\SHP633-303\_SAP\_Draft\_V1.0\_20171023

Author: [REDACTED]

Version Number:

Draft V1.2

Version Date:

16Jan2018

Template No: CS\_TP\_BS016 – Revision 3

Reference: CS\_WI\_BS005

Effective Date: 01May2012

Copyright © 2012 Quintiles Transnational Corp. All rights reserved.

The contents of this document are confidential and proprietary to Quintiles Transnational Corp. Unauthorized use, disclosure or reproduction is strictly prohibited.

### **8.3. MISSING DATA**

Missing data will in general not be imputed. However, partial dates will contribute to the analysis as described in Appendix 2. All available data will be included in the safety analysis.

Details for the imputation algorithm for the missing endpoint values for PS parameters (volume, calories and etc.) will be described in Section [16.1.1](#) of this analysis plan.

### **8.4. MULTIPLE COMPARISONS/ MULTIPLICITY**

Given the small sample size, no hypothesis testing will be conducted. Therefore, there will be no adjustment for alpha level.

### **8.5. EXAMINATION OF SUBGROUPS**

No subgroup analysis will be performed for prospective data.

## **9. OUTPUT PRESENTATIONS**

[APPENDIX 1](#) shows conventions for presentation of data in outputs. The output templates provided together with this SAP describe the presentations for the analyses of this study based on Shire internal standards TFLs4ShireFinalV6.0. The format and content of the summary tables, figures and listings (TFLs) will be provided by Quintiles Biostatistics.

## **10. DISPOSITION AND WITHDRAWALS**

All subjects who provide informed consent for prospective data collection in the extension study will be accounted for in the analyses. After signed consent (and informed assent, if applicable), a subject will be considered enrolled in the study if the subject meets all of the inclusion criteria at the screening. Teduglutide treatment eligibility does not impact study eligibility.

If the investigational product is discontinued prematurely during a teduglutide treatment cycle and the subject wishes to remain in the study, the evaluations listed for the EOT visit are to be performed. A 4-week follow-up period will ensue, consisting of weekly telephone visits (CxW25-27) and the week 28 clinic visit (CxW28). The subject would then enter a NTT period and could be evaluated for subsequent teduglutide treatment eligibility according to the study

Document:	\quintiles.net\Enterprise\Apps\sasdata\SASa\sas\Shire\Teduglutide\ZXA48914\Biostatistics\Documentation\SAP\SHP633-303_SAP_Draft_V1.0_20171023		
Author:	[REDACTED]	Version Number:	Draft V1.2

Template No: CS\_TP\_BS016 – Revision 3  
Effective Date: 01May2012

Reference: CS\_WI\_BS005

Version Date:  
16Jan2018

Copyright © 2012 Quintiles Transnational Corp. All rights reserved.  
The contents of this document are confidential and proprietary to Quintiles Transnational Corp. Unauthorized use, disclosure or reproduction is strictly prohibited.

schedules. The reason for permanent treatment discontinuation will be captured.

The reason(s) for permanent discontinuation of treatment and/or withdrawal from the study must be determined by the investigator, and recorded in the subject's medical record and in the electronic case report form (eCRF). If a subject is withdrawn for more than one reason, each reason should be documented in the source document, and the most clinically relevant reason should be entered in the eCRF. Overall reasons for discontinuation of treatment and withdrawal from study will be summarized separately based on the following categories:

- Adverse event
- Protocol deviation
- Lack of efficacy
- Physician decision
- Withdrawal by subject
- Withdrawal by parent/guardian
- Lost to follow-up
- Pregnancy
- Death
- Other

The ongoing subjects will be counted in the table for interim analysis.

Protocol deviations as obtained from a clinical trial management system (CTMS) will be assessed throughout the study. All identified deviations will be reported in the CTMS. Protocol deviations from the CTMS will be coded to categories and provided as part of the CTMS transfer to Biostatistics. Protocol deviation categories from CTMS include:

1. Informed Consent Criteria
2. Eligibility and Entry Criteria
3. Concomitant Medication Criteria
4. Laboratory Assessment Criteria
5. Study Procedures Criteria
6. Serious Adverse Event Criteria
7. Randomization Criteria (Not applicable to this study)
8. Visit Schedule Criteria
9. Investigational Product Compliance

Document: \\quintiles.net\Enterprise\Apps\sasdata\SASa\sas\Shire\Teduglutide\ZXA48914\Biostatistics\Documentation\SAP\SHP633-303\_SAP\_Draft\_V1.0\_20171023

Author: [REDACTED]

Version Number:

Draft V1.2

Version Date:

16Jan2018

Template No: CS\_TP\_BS016 – Revision 3

Effective Date: 01May2012

Reference: CS\_WI\_BS005

Copyright © 2012 Quintiles Transnational Corp. All rights reserved.

The contents of this document are confidential and proprietary to Quintiles Transnational Corp. Unauthorized use, disclosure or reproduction is strictly prohibited.

---

- 10. Efficacy Criteria
- 11. Administrative Criteria
- 12. Source Document Criteria
- 13. Regulatory or Ethics Approvals Criteria
- 14. Other Criteria

The presentation of planned listings will include the following:

- Subject disposition (SRN set)
- Study Inclusion criteria violations (SRN set)
- Treatment Eligibility Criteria
- Follow-up Period Escape Criteria
- Protocol deviations

The following summary tables are planned for presentation:

- Subject disposition (SRN set)
- protocol deviations,

